6.1 Treatments Administered

Dose information for each treatment group for the TP is provided in Table 6. Study treatment will be supplied in blister card kits. The capsules will be arranged into sets to be taken in the morning and in the evening, approximately 12 hours apart. If a subject forgets a dose, but remembers within 4 hours of the expected dose, the dose should be taken. If the missed dose is discovered more than 4 hours after it should have been taken, that dose should be not be taken and the next scheduled dose should be taken at the usual time.

Table 6: Selection and Timing of Dose

| Study Treatment | Unit dose strength(s)/ Dosage level(s) | Dosage formulation Frequency of Administration | Route of Administration |
|------------------------|---|--|----------------------------|
| 12 mg QD BMS-986165 | 3 mg | 4 active capsules QD in the morning; and 4 placebo capsules QD in the evening | Oral |
| 6 mg BID BMS-986165 | 3 mg | 2 active and 2 placebo capsules; BID | Oral |
| 3 mg BID BMS-986165 | 3 mg | 1 active and 3 placebo capsules; BID | Oral |
| Placebo | Not applicable | 4 placebo capsules; BID | Oral |

BID = twice daily; QD = once daily

6.2 Method of Treatment Assignment

At the time of the screening visit, immediately after informed consent is obtained and before any study-related procedures are performed, the investigative site will access the enrollment option using IRT for assignment of a subject number (including subjects not subsequently randomized or treated). This number will be unique across all sites. Enrolled subjects, including those not dosed, will be assigned sequential subject numbers. The subject number may not be used for any other subject. If a potential subject is rescreened, they will be given a new identification number.

CRS and the PRA medical monitor will confirm subject eligibility based on criteria in [Section 5](#). Eligible subjects will be centrally randomized using IRT to receive oral treatment with BMS-986165 12 mg QD, 6 mg BID, 3 mg BID, or placebo BID according to a computer-generated block randomization scheme and in accordance with stratification criteria. Randomization numbers will be assigned prior to dosing.

Before the study is initiated, each user (at investigative sites) will receive log-in information and directions on how to access the IRT. Study treatment will be dispensed at study visits as shown in [Section 1.3](#) (Schedules of Activities).

6.3 Blinding

6.3.1 Maintaining the Blind

Blinded treatment assignments will be managed using IRT. All capsules (BMS-986165 3 mg and placebo) are identical in appearance, and they will be supplied in blister packs with each daily dose made up of the appropriate combination of active and/or placebo capsules to provide the correct

treatment (as shown in [Table 6](#)). Investigative site staff, Sponsor and designee personnel, the [REDACTED] ([Section 4.1.1](#)), and subjects and their families will remain blinded to treatment assignments.

Blinding of treatment assignment is critical to the integrity of this clinical study. However, in the event of a medical emergency or pregnancy in an individual subject in which knowledge of the IP is critical to the subject's management, the blind for that subject may be broken by the investigator. The subject's safety takes priority over any other considerations in determining if a treatment assignment should be unblinded.

Before breaking the blind of an individual subject's treatment, the investigator should determine that the unblinded information is necessary, ie, that it will alter the subject's immediate management. In many cases, particularly when the emergency is clearly not related to the IP, the problem may be properly managed by assuming that the subject is receiving active product. It is highly desirable that the decision to unblind treatment assignment be discussed with the [REDACTED] medical monitor, but the investigator always has ultimate authority for the decision to unblind. The principal investigator should only call in for emergency unblinding AFTER the decision to discontinue the subject has been made.

For information on how to unblind in an emergency, consult the IRT manual.

In case of an emergency, the investigator has unrestricted access to randomization information via IRT and is capable of breaking the blind through the IRT system without prior approval from the Sponsor. After the unblinding, the investigator shall notify the [REDACTED] medical monitor and/or study director. The method of unblinding for emergency purposes is described in the IRT manual. Subject information and the reason for the blind being broken must be recorded on the appropriate study status page of the electronic case report form (eCRF). After unblinding via IRT, the investigator shall notify the [REDACTED] medical monitor. In cases of accidental unblinding, contact the [REDACTED] medical monitor and ensure every attempt is made to preserve the blind. Any request to unblind a subject for nonemergency purposes must be discussed with the [REDACTED] medical monitor prior to unblinding.

Designated staff of Bristol-Myers Squibb Research & Development (or designee) may be unblinded (obtain the randomization codes) prior to database lock to facilitate the bioanalytical analysis of pharmacokinetic samples. A bioanalytical scientist in the Bioanalytical Sciences department of Bristol-Myers Squibb Research & Development (or a designee in the external central bioanalytical laboratory) will be unblinded to (may obtain) the randomized treatment assignments in order to minimize bioanalytical analysis of samples.

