8.6 Pharmacokinetics

The PK of BMS-986165 and metabolites (if applicable) will be derived from plasma concentration versus time.

Plasma samples will be analyzed for BMS-986165 and BMT-153261 by a validated assay. Pharmacokinetic samples collected from subjects who receive placebo will not be analyzed. Individual subject PK parameter values will be derived by noncompartmental methods by a validated PK analysis program. Actual times will be used for the analyses. In addition, plasma samples will be archived for potential metabolites analysis, if the need arises and to the extent possible. Detailed instructions for PK blood collection, labeling, processing, storage, and shipping will be provided to the site in the Study Reference Manual.

The PK parameters to be assessed include:

| | |
|---------------------|---|
| C _{max} | Maximum observed plasma concentration |
| T _{max} | Time of maximum observed plasma concentration |
| C _{trough} | Trough observed plasma concentration |

The area under the concentration-time curve in one dosing interval (AUC[TAU]) will be calculated if possible.

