9.3.3.2 Pharmacodynamics

Pharmacodynamic evaluation is a secondary endpoint. Selected PD endpoints such as IRG expression, C3, C4, and anti-dsDNA will be summarized by treatment and timepoint, and their corresponding changes and percent change from baseline will be calculated and summarized. Change from baseline in lymphocyte count, serum or plasma proteins, genome-wide RNA expression, lymphocyte subsets and activation status, etc, will be summarized by time. Baseline values will be defined as the last measurement before the first dose.

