5.3 Unblinding Information

Investigative site staff, Sponsor and designated personnel, and subjects and their families will remain blinded to treatment assignments. After the week 48 database lock, the Sponsor and designated personnel will be unblinded. Those subjects who are enrolled or will enroll in study IM011-074 will continue to remain blinded to their treatment assignment (including investigative site staff and subjects' families) in this study after the week 48 database lock. Those subjects who do not enroll or will not enroll in study IM011-074 may be unblinded to their treatment assignment (including investigative site

Sponsor: Bristol-Myers Squibb
Protocol no: IM011021

staff) after the week 48 database lock. However, if there is a medical emergency or pregnancy where knowledge of investigational product (IP) is critical to the subject's management the blind may be broken by the Investigator.

The Data Monitoring Committee (DMC) provides oversight of safety consideration throughout the study. A separate unblinded team, comprised of an unblinded Independent Reporting Statistician (IRS) and unblinded programmer(s), will produce output for the DMC using masked treatments. Treatment decodes may only be requested by DMC Chair and will be provided by the IRS. Data summaries and listings will be transmitted via a secure portal by IRS to only the DMC members. Additional details regarding the DMC process and unblinding are provided in the DMC charter.

Designated staff of BMS may be unblinded prior to database lock to facilitate the bioanalytical analysis of PK and biomarker samples and immunogenicity.

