8.4 Biomarker

The Biomarker population is defined as all randomized subjects who receive at least one dose of study treatment and have at least one post-treatment biomarker measurement. Subjects will be analyzed according to the treatment received.

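### SAP 5.3 allows sponsor staff to be unblinded before database lock for biomarker assays, where Protocol 6.3.1 gives that permission for pharmacokinetic samples

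*Protocol*

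**What the plan says.** Protocol 6.3.1 keeps site staff, sponsor and designee personnel, and subjects blinded, and then makes an exception for bioanalysis. Designated sponsor research staff (or a designee) "may be unblinded (obtain the randomization codes) prior to database lock to facilitate the bioanalytical analysis of pharmacokinetic samples". The next sentence adds that a bioanalytical scientist, in-house or at the external laboratory, "will be unblinded to (may obtain) the randomized treatment assignments in order to minimize bioanalytical analysis of samples".

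SAP 5.3 restates the exception with a wider scope. Designated sponsor staff "may be unblinded prior to database lock to facilitate the bioanalytical analysis of PK and biomarker samples and immunogenicity".

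On what is assayed in whom, Protocol 8.6 states: "Pharmacokinetic samples collected from subjects who receive placebo will not be analyzed". The SAP defines its Biomarker population (8.4) as "all randomized subjects who receive at least one dose of study treatment and have at least one post-treatment biomarker measurement", with no restriction to the active arms.

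On the standing of these measures, Protocol 9.3.3.2 states "Pharmacodynamic evaluation is a secondary endpoint" and continues: "Selected PD endpoints such as IRG expression, C3, C4, and anti-dsDNA will be summarized by treatment and timepoint".

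**The concern.** The SAP is written for the protocol revision of 15 April 2020 (SAP 1.0 and 3.0), yet it allows unblinding that the protocol's bioanalysis exception does not name. A SAP should implement the protocol's blinding rules and should not loosen them without a stated reason.

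What is at stake is the blinded measurement of the PD endpoints. Some of this work leaves room for judgement: how gene expression is normalised, how cytometry gates are set, and which runs are repeated or rejected. IFN status is a further case. SAP 13.0 assigns high or low from screening samples, and that label defines a subgroup of the primary endpoint (SAP 11.7.4) and underlies a PD endpoint in Protocol Table 4, clinical response by IRG status at Week 32. The visible text gives no cutoff and does not require blinded assignment. If people making these choices know the arm, the double-blind claim for the PD results is weaker than it needs to be.

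**Working it through.** No arithmetic applies, because the point rests on no sample size, rate or error level. The check is a comparison of text.

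**Step 1: scope of the permission.**

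| | Protocol 6.3.1 | SAP 5.3 |
|---|---|---|
| PK samples | named | named |
| Biomarker samples | not named | named |
| Immunogenicity | not named | named |
| Reason for the access | to reduce the assay load | to facilitate the assays; nothing further |

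The SAP adds two categories. The legible items in its change lists (SAP 5.4 to 5.6) record no change to unblinding. The nearest are general entries that the PK and biomarker analyses were updated.

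**Step 2: does the protocol's second sentence already cover biomarkers?** It refers to samples without a qualifier, so the words alone could reach them. But it follows directly on the PK sentence, and its aim is to minimise bioanalysis. That aim fits PK. Placebo PK samples are left unassayed (Protocol 8.6), and SAP 8.5 gives the laboratory the randomization file so that it runs plasma from active-arm subjects only. The natural reading is PK.

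**Step 3: does the PK reason carry over to biomarkers?** Protocol 8.9 has biomarker samples taken, as a rule, from everyone in the trial, apart from the Day 2 or 3 samples. The Biomarker population in SAP 8.4 includes placebo subjects. SAP 13.0 summarizes the markers by arm, and by IFN status within arm. No placebo assay is saved by knowing the code, so the reason does not carry over.

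**Step 4: is another reason or a safeguard visible?** Protocol 4.1.1, 6.3.1, 8.6, 8.9, 9.3.3.2 and 9.3.4 and SAP 5.3 to 5.6, 6.6, 8.5, 13.0 and 14.0 were compared. None gives a different reason for unblinding biomarker work. None says that biomarker assay staff stay blinded.

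**Step 5: which measures are exposed?** SAP 6.6 places complement, anti-dsDNA and the RNA for IRG expression among the biomarker samples. These match the markers that Protocol 9.3.3.2 names as PD endpoints: IRG expression, C3, C4 and anti-dsDNA. SAP 13.0 computes change in individual IRGs from normalised values, so there is a processing step. Flow cytometry is also exposed, but only in a substudy (SAP 6.6).

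**The case against.** Several objections have force.

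**Permissive wording.** SAP 5.3 says that staff *may* be unblinded. It does not show that anyone was. This stands: the point concerns what the plan allows.

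**Other routes to the codes.** The protocol also allows emergency unblinding, unblinded DMC summaries and an optional interim look by a separate sponsor team (SAP 14.0 says that no interim analysis will be done). This stands, so the point is confined to the bioanalysis exception.

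**Weight of the PD endpoints.** Protocol Table 4 lists PD apart from the secondary efficacy endpoints. The visible PD analyses are summaries and changes from baseline, with no visible hypothesis test. This lowers the stakes but does not remove the mismatch.

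**Redaction.** Schedule rows and parts of the biomarker list are blacked out. A reader might infer that immunogenicity is a mistake because no such sample is visible, or that no biomarker assay could ever need the codes. Neither inference is safe.

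**The primary endpoint.** A reader might go further. Low complement and increased DNA binding score 2 points each in SLEDAI-2K, and 2 + 2 = 4 equals the SRI(4) reduction, so unblinded assays might seem to threaten the primary result. The documents do not support that step. The SLEDAI-2K total is taken from the eCRF (SAP 6.1 and 11.7.1). Protocol 8.2 lists C3, C4 and anti-dsDNA among the disease-activity laboratory tests, and Protocol 8.9 says that individual biomarker results are not shared with investigators. Nothing shows that the sponsor staff covered by SAP 5.3 produce the values that are scored. Both items are present or absent against a laboratory limit, so a 4-point effect would need both to flip in the same subject.

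**Extent.** Nor do the documents support the reading that all biomarker values in about 360 subjects are affected. Cytometry is a substudy, and the permission may not have been used.

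**Conclusion.** The mismatch is real. SAP 5.3 allows pre-lock unblinding for biomarker and immunogenicity bioanalysis that Protocol 6.3.1, read in context, does not. The reason that supports the PK exception does not extend to biomarkers measured in all arms, and no visible text supplies another.

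The consequence is limited. The PD measures, and cytometry in its substudy, could be processed by staff who know the arm. The size of any bias cannot be derived: the documents do not say which assays are automated, which involve judgement, or who runs them. No effect on SLEDAI-2K or SRI(4) is established.

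The conclusion rests on reading the protocol's unqualified second sentence as referring to PK, and on the redacted text containing neither a reason for the wider access nor a blinding safeguard. It is worth correcting because it is an avoidable source of bias in measures that the protocol calls a secondary endpoint, and the correction costs very little.

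**What to change.** In SAP 5.3, restrict pre-lock unblinding to PK bioanalysis, in line with Protocol 6.3.1. Add that staff who run, normalise, gate, repeat or reject biomarker assays, or who assign IFN status, stay blinded until the Week 48 database lock.

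If a specific assay does need the codes, amend the protocol to name the assay and state the reason, and keep the unblinded staff separate from those who process the data.

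The main route costs a sentence or two in the SAP and an instruction to the assay staff, with no patients or samples. The exception route adds a protocol amendment and the small task of documenting the separation. If access has already been given under the present wording, the blinding statement cannot be made for those staff, and the access should be recorded instead.

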6.4 Dosage Modification

There is no provision for dose modification of study treatment. Titration of CS and its use as rescue therapy are discussed in [Section 6.7.3](#) [REDACTED]. Modification of other background SLE therapies or dose regimens is not permitted during study participation. Subjects should continue to take their assigned treatment even if they experience flares and/or are unable to taper their CS dose, unless any of the criteria in [Section 7.1](#) are met.

If a subject interrupts treatment due to an AE, study treatment can be restarted in consultation with the [REDACTED] medical monitor.

6.5 Preparation/Handling/Storage/Accountability

The IP should be stored in a secure area according to local regulations. It is the responsibility of the investigator to ensure that IP is only dispensed to study subjects. The IP must be dispensed only from official study sites by authorized personnel according to local regulations.

The study treatment is stored in accordance with the environmental conditions (temperature, light, and humidity) required by BMS. If concerns regarding the quality or appearance of the study treatment arise, the study treatment should not be dispensed and BMS should be contacted immediately.

Investigational product documentation (whether supplied by BMS or not) must be maintained that includes all processes required to ensure drug is accurately administered. This includes documentation of drug storage, administration, and, as applicable, storage temperatures, reconstitution, and use of required processes (eg, required diluents, administration sets).

Further guidance and information for final disposition of unused study treatment are provided in [APPENDIX 1](#).

6.5.1 Retained Samples for Bioavailability/Bioequivalence

Not applicable.

6.6 Treatment Compliance

Study treatment compliance will be periodically monitored using standard drug accountability procedures (comparing the number of capsules returned to number dispensed, considering the expected regimen and any reported missed doses). Drug accountability will be reviewed by the investigative site staff at each visit to confirm treatment compliance. Site staff will discuss any discrepancies with the subject and remind the subject of the importance of compliance with the assigned regimen. A real-time monitoring platform may be used.

6.7 Concomitant Therapy

All medications ever taken for SLE including topical, discontinued, and investigational therapies must be recorded; medications with dose changes may record the overall dates with last dose used. All medications taken from within 4 weeks before screening until 30 days after the last dose of study treatment (inclusive) must be recorded on the eCRF. Other than existing treatment for SLE (with restrictions as described in the eligibility criteria [[Section 5.1](#)]), concomitant medications (prescription, over-the-counter [OTC], or herbal) should only be administered during the study if they are prescribed for treatment of specific clinical events.

6.7.1 Prohibited and/or Restricted Treatments

Restrictions and prohibitions on prior and concomitant medications are as follows:

1. Prior exposure to BMS-986165 or other TYK2 inhibitors is prohibited.
2. Rescue therapy other than prednisone or equivalent is prohibited.

3. Use of intramuscular, intra-articular, intrabursal, and IV CS is prohibited (Inclusion Criterion 3)b); [Section 5.1](#)). Initiation during the study of short-term treatment with inhaled CS for a nonlupus medical condition must be discussed with the [REDACTED] medical monitor. Topical CS use may not be initiated during treatment. Modified-release CS formulations are prohibited.
4. Topical NSAID use may not be initiated during treatment. No more than 1 oral NSAID may be used during the study. Aspirin is allowed (in addition to a single NSAID and topical NSAIDs) at stable doses no higher than 325 mg/day throughout the study. NSAIDs may not be used on an as-needed basis. Although regimens are required to be stable throughout the study, NSAID dosing may be decreased or discontinued if due to NSAID toxicity. Adjustments in NSAID regimens must be discussed with the [REDACTED] medical monitor.
5. Use of opioid analgesics is prohibited unless criteria outlined in Exclusion Criterion 3)e); [Section 5.2](#), are met.
6. Use of cyclophosphamide (including ophthalmic) or any IV, intrabursal, intratendinous sheath, intramuscular, subcutaneous, intra-articular, or biologic agent is prohibited. Required discontinuation periods for immunomodulatory and biologic drugs before the signing of informed consent are provided in [APPENDIX 7](#). For similar agents not listed, the discontinuation period is 4 weeks or 5 half-lives, whichever is longer, and must be discussed with the [REDACTED] medical monitor.
7. Live vaccines are prohibited during the TP or within the 2 months after the last dose. Heat-killed or otherwise inactivated or protein vaccines such as influenza and pneumococcal vaccines may be received at any time on study. Any other inactivated vaccines (eg, tetanus, etc) should be used according to local guidelines during the TP (Exclusion Criterion 4)g); [Section 5.2](#)).
8. Exposure to any investigational drug or placebo within 12 weeks or 5 half-lives (whichever is longer) before screening is prohibited (Exclusion Criterion 3)f); [Section 5.2](#)
9. Use of any other drugs, including OTC medications and herbal preparations, within 1 week before the first dose of study treatment is prohibited, except medications cleared by the [REDACTED] medical monitor

6.7.2 Existing Therapies for Systemic Lupus Erythematosus

All subjects will continue their existing SLE treatment(s) during the study (if the treatment complies with the eligibility criteria; [Section 5](#)). The dose and regimen of background SLE treatments must not change during study participation. Details of permissible therapies are as follows:

- At least 1 background agent as specified in Inclusion Criterion 3)a) ([Section 5.1](#)); use of more than 1 immunosuppressant in combination is NOT permitted.
- CS therapy with prednisone or equivalent as specified in Inclusion Criterion 3)b) ([Section 5.1](#)); see restrictions in [Section 6.7.1](#). CS tapering [REDACTED] are described in [Sections 6.7.3](#) [REDACTED]
- Chronic NSAID therapy as specified in Inclusion Criterion 3)c) ([Section 5.1](#))
- Stable preexisting topical CS therapy as specified in Inclusion 3)b) ([Section 5.1](#))

6.7.3 **Corticosteroid Tapering**

For subjects receiving prednisone or equivalent, the dose of CS must be stable for 2 weeks before the screening visit (signing of informed consent) and throughout the SP until randomization. Up to 30 mg/day prednisone or equivalent is permitted during the SP (and for the preceding 2 weeks). Rules for CS tapering are as follows:

- Tapering of CS may begin at any time after the first dose of IP on Day 1.
- For subjects receiving > 7.5 mg/day prednisone or equivalent, tapering must start by Week 8.
- For all subjects, the CS dose must be ≤ 7.5 mg prednisone or equivalent by Week 20 (if this is not possible, the subject will remain on treatment, but will be a nonresponder for analysis purposes).
- Investigators must assess the subject's suitability for CS taper at each visit (taper is not required to start until Week 8), and the last day for CS taper is the Week 20 visit.
- The CS dose must be tapered (beginning by Week 8 and continuing until the Week 20 visit) unless any of the following are observed:
 - New or worse BILAG or SLEDAI-2K activity for any of the following parameters: central nervous system, vasculitis, myositis, cardiorespiratory, gastrointestinal, ophthalmologic, renal, or thrombocytopenia
 - New or worsening hemolytic anemia
 - CLASI activity score ≥ 10
 - Active joint count of 8 or more joints with both tenderness AND swelling
- Tapering is required if disease activity has not worsened. The investigator must justify any decision not to taper. Criteria met or not met for taper will be documented on the eCRF at each appropriate visit.
- The CS dose must remain stable from Week 20 until Week 32. Tapering may be resumed at the Week 32 visit according to the same parameters as earlier in the study. The last day for CS taper is the Week 40 visit, and the CS dose must remain stable from Week 40 until Week 48.

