9.3.1.2 Nonresponders

Subjects will be considered nonresponders in the TP for the responder-type efficacy endpoints (ie, BICLA and SRI) in the primary and secondary analyses at weeks 32 and 48, respectively, if they meet any of the following criteria:

- Requires CS dose > 7.5 mg/day prednisone or equivalent after Week 20
- Requires CS rescue therapy beginning after the Week 8 visit
- Requires more than 1 burst of CS rescue therapy
- Requires dose increase in background immunosuppressant or antimalarial medication
- Requires treatment with medications prohibited by the protocol ([Section 6.7.1](#) and [APPENDIX 7](#))
- Discontinues treatment before the assessment timepoint or has a missing value for the particular endpoint

Nonresponder definitions for other time points will be provided in the SAP.

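### For a subject on more than 7.5 mg/day of steroid who is stable or improving but still above an absolute skin or joint threshold, Protocol 6.7.3 both lifts and imposes the duty to taper, and the reading followed can decide whether that subject can still count as a responder.

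*Protocol*

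**What the plan says.** Protocol 6.7.3 sets the taper rules in consecutive bullets.

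- The general duty and its exemptions: "The CS dose must be tapered (beginning by Week 8 and continuing until the Week 20 visit) unless any of the following are observed". The organ-activity and hemolytic-anemia items on the list each require new or worsening disease. The other two, "CLASI activity score ≥ 10" and "Active joint count of 8 or more joints with both tenderness AND swelling", are levels with no reference to baseline.
- The bullet after the list: "Tapering is required if disease activity has not worsened". It continues: "The investigator must justify any decision not to taper".
- A start date with no exemption attached: "For subjects receiving > 7.5 mg/day prednisone or equivalent, tapering must start by Week 8".
- A Week 20 ceiling of 7.5 mg with a stated consequence: "if this is not possible, the subject will remain on treatment, but will be a nonresponder for analysis purposes".

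Tapering may resume between Weeks 32 and 40 on the same parameters, so the same bullets apply again before Week 48.

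The consequence for analysis is in Protocol 9.3.1.2, where one nonresponder criterion is "Requires CS dose > 7.5 mg/day prednisone or equivalent after Week 20". SAP 11.7.1 applies the 7.5 mg/day limit to the primary endpoint whatever SRI response was observed, and SAP 11.7.2.2 repeats it for BICLA at Week 48.

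Two SAP sections describe the taper differently. SAP 5.0 says it must start by Week 8 and gives no exemption. SAP 11.5.2 lists a CLASI activity score of at least 10 and at least 8 tender-and-swollen joints as stand-alone reasons why the dose was not reduced.

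**The concern.** A site reading the exemption list may hold the steroid dose of a patient whose skin disease has halved but is still above the threshold. A site reading the next bullet must taper the same patient. Neither document says which instruction governs.

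This matters statistically because the steroid dose after Week 20 is part of the response definition. If the dose stays above 7.5 mg/day, the patient is a nonresponder by imputation; if it comes down, the observed SRI(4) result counts. Part of the primary outcome could then reflect how a site read the protocol.

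The group concerned can exist by design. Inclusion criterion 3b allows up to 30 mg/day at screening, everyone in the stratum of 10 mg/day or more is above 7.5 mg/day, and entry requires joint involvement and/or rash.

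**Working it through.** **Step 1: apply each rule to the same subject.** Take a subject whose CLASI activity has fallen from 24 to 12, or who has a steady 9 active joints, with no other listed finding.

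| Rule in Protocol 6.7.3 | Test | Result |
|---|---|---|
| Exemption list | CLASI 12 is at least 10; 9 joints is at least 8 | No duty to taper |
| Following bullet | Disease has not worsened | Taper required |

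The results are opposite. The bullet on starting by Week 8 and SAP 5.0 contain no exemption; SAP 11.5.2 fits the list.

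**Step 2: follow each result to the primary endpoint.**

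| Steroid dose | Reading followed | Status at Weeks 32 and 48 |
|---|---|---|
| Above 7.5 mg/day | Exempt, and dose held | Imputed nonresponder; response impossible |
| Above 7.5 mg/day | Tapered to 7.5 mg or less by Week 20 | Observed result counts; response possible |
| 7.5 mg/day or less, or none | Either | Dose criterion not triggered; no effect |

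Response in the second row is feasible. Rash carries 2 SLEDAI-2K points, so a 4-point fall can come from other items, and activity can also fall between Week 20 and Week 32.

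**Step 3: other endpoints.** SRI(4) and BICLA at Week 48 use the same limit. LLDAS has its own 7.5 mg/day criterion (SAP 11.7.2.4). Joint counts are set to missing at visits where the imputation criteria are met (SAP 11.7.2.5).

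**Step 4: the plan's power figure, for context.** Protocol 9.1 and SAP 5.1 state at least 84% power for a 20-point difference with 90 per arm. The BID alpha of 0.04 is given in the protocol's summary of changes. The placebo rate and exact contrast are not visible, so I assumed placebo rates of 20% to 50%.

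Power = Φ[(d − z × SE0) / SE1], where d is the difference, z the two-sided critical value at 0.04, SE0 the standard error under the pooled rate and SE1 the standard error under the two separate rates.

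- One BID arm against placebo (90 and 90): 74.0% to 81.5%.
- Both BID arms pooled against placebo (180 and 90): 85.8% to 91.1%.

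The pooled contrast agrees with the stated figure. Without the missing inputs it cannot be called right or wrong, and this point does not depend on it.

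**Step 5: an illustration of size.** Assume a fraction f of would-be responders in every arm becomes nonresponders. The difference becomes 20 × (1 − f) points. Power is for the pooled BID contrast at alpha 0.04, with both arms' rates multiplied by (1 − f).

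| f (assumed) | Difference, points | Power, placebo 30% (assumed) | Power, placebo 40% (assumed) |
|---|---|---|---|
| 0% | 20 | 87.0% | 85.8% |
| 5% | 19 | 83.8% | 81.9% |
| 10% | 18 | 80.2% | 77.6% |
| 15% | 17 | 76.3% | 72.9% |
| 20% | 16 | 72.0% | 68.0% |

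Neither document gives f.

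**The case against.** The best defence is that the sentence about disease not having worsened is loose shorthand for the list just above it. The same bullet has sites record on the eCRF whether the taper criteria were met, which naturally refers back to the list, and SAP 11.5.2 takes the two absolute thresholds from the steroid forms as reasons in their own right. This makes the exemption reading the likelier intention. It does not remove the conflict: on the words, the two absolute items do nothing for a stable or improving subject if the later sentence governs, and nothing ranks the two.

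Four stronger conclusions that a reader might draw are not supported.

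- **That the Week 20 ceiling is a third contradiction.** It is not. It provides for subjects who cannot reach 7.5 mg: they stay on treatment and count as nonresponders.
- **That an exempt subject necessarily stays above 7.5 mg/day.** The list lifts an obligation and does not forbid tapering, which may begin at any time after the first dose. A required taper can also fail.
- **That sites demonstrably diverge, or that the arms are biased against each other.** Divergence is possible but not shown. Assignment is randomized and blinded, and the mechanism described is attenuation.
- **That a particular loss in the treatment difference can be stated.** The affected share is unknown. Step 5 also treats affected subjects as would-be responders at the same rate in every arm; a subject who keeps 8 or more active joints retains the 4 SLEDAI-2K points for arthritis and is less likely to reach SRI(4).

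It is also fair that sensitivity analyses 1 and 2 in SAP 11.7.1 do not impute nonresponse for steroid dose. They would expose part of the effect. They do not isolate it, because each drops the other prohibited-medication criteria too (analysis 1 also drops treatment discontinuation), and the primary analysis keeps the dependence.

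**Conclusion.** The contradiction is real on the current text and narrow in scope. It concerns subjects above 7.5 mg/day prednisone equivalent who are stable or improving but still have CLASI activity of 10 or more, or 8 or more tender-and-swollen joints. For them, the reading a site follows can decide whether a response can still be counted in the primary analysis. It does not decide whether response occurs, and it changes nothing for subjects at or below 7.5 mg/day.

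The size is unknown. The range of 19 to 16 points rests wholly on the assumed 5% to 20% and on equal effect in all arms. No stated sample-size or power figure is shown to be wrong. The case for acting is that the rule cannot be followed as written, it feeds the primary endpoint, and it is cheap to repair.

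**What to change.** The clinical team should reconcile the exemption list and the bullet that follows it in Protocol 6.7.3 into one taper rule with a stated priority, and make the Week 8 start bullet consistent with it. SAP 5.0 and the list of reasons for no reduction in SAP 11.5.2 should then be aligned. Which rule to adopt is a clinical decision, and none is proposed here.

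The cost is a clarification letter or amendment wording, site retraining and a small SAP edit. For taper decisions already taken, the reasons collected under SAP 11.5.2 could be set against baseline values to count, by arm, the subjects above 7.5 mg/day after Week 20 who met an absolute threshold without worsening. That would replace the assumed range with an observed upper limit on the number affected.
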